4	< 0.5	
 Re-check ANC at least weekly If resolved to grade 1, re-check ANC 3 days after rechallenge with dabrafenib and then 1 week later. 	
 Discontinue or hold until return to grade 1, then reduce dabrafenib by one dose level. 1st recurrence discontinue dabrafenib

Table 4: Dose Modification and Guide lines for Manage ment of Fever

	Definition	Dose Mod ificati on Algorithms	Dabrafeni b Dose Adjustment
Co mplicated fever. ($\geq 38.5^{\circ}\text{C}$ or 101.3°F)	Grade ≥ 3 or any grade with signs and symptoms including; rigors , dehydration, hypotension, dizzines s or wea kness	
 • Subject must be evaluated in clinic • Labs : Obtain blood sample to assess ANC, s erum creat inine and BUN if samp le was not collected within 3 days of the fever. • Evaluate for signs and symptoms of infect ion and cons ider work up as clin ically indicated. • If signs and symptoms of dehydration occur, cons ider intravenous hydration. • When restarting drug, adminis ter acetaminophen 500 mg or ibuprofen 400 mg (or suitable alternative) prophylactically BID with study drug for 2-3 days. • Re-check ANC 1 week after the start of fever; encourage subject to take oral temperature daily for 4 weeks after restarting dabrafenib. 	
 • Interrupt dabrafenib immed iately and hold until fever resolves to $<38.0^{\circ}\text{C}$ or 100.4°F and accompanying symptoms resolve • At rechallenge reduce dose of dabrafenib by one dose level.
Uncomp licated Fever ($\geq 38.5^{\circ}\text{C}$ or 101.3°F)	defined as grade ≤ 2 without signs and symptoms as des cribed above	
 • Encourage oral hydration. • If subject is seen in the clinic, obtain blood sample to assess ANC, s erum creat inine and BUN if samp le was not collected within 3 days of the fever • Evaluate for signs and symptoms of infect ion and cons ider work up as clin ically indicated. • If signs and symptoms of dehydration occur, follow a lgorithm for complicated fever. • When restarting drug, adminis ter acetaminophen 500 mg or ibuprofen 400 mg (or suitable alternative) prophylactically BID 	
 • Hold until fever resolves to $<38.0^{\circ}\text{C}$ or 100.4°F. • Dabrafenib may be restarted at the original dose level or reduced one dose level as clin ically indicated.

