b. Life style modifications include; avoidance of excessive temperatures, exercise, and ill-fitting clothing/shoes. Use of soft slippers (Tempurpedic or Crocs), friction-relieving measures (calfskin,

- gels).
 c. HSRF usually resolves within 2-4 weeks of drug cessation.

Table 7: Renal Insufficiency Guidelines

Creatinine	Guidelines for Management
For subjects with serum creatinine increase > 0.2 mg/dL but ≤ 0.5 mg/dL above baseline:	
 1. Continue dabrafenib and re-check serum creatinine within 1 week 2. If subject has fever ($T \geq 38.5C$): treat pyrexia as per guidelines (please note NSAIDs can induce renal insufficiency, especially in subjects with dehydration); encourage oral fluids 3. If elevation in serum creatinine persists beyond 1 week, please contact medical monitor
For subjects with serum creatinine rise > 0.5 mg/dL above baseline or serum creatinine > 2 mg/dL:	
 1. Interrupt dabrafenib 2. If subject has fever ($T \geq 38.5C$): treat pyrexia as per guidelines (please note NSAIDs can induce renal insufficiency, especially in subjects with dehydration); consider IV hydration 3. Follow serum creatinine at least twice weekly (or consider hospitalization if serum creatinine cannot be monitored frequently) 4. Consider renal consultation 5. If serum creatinine returns to baseline, may restart study treatment at the same dose, or reduced by one dose level at the investigator's discretion. 6. Consider renal biopsy if clinically indicated, for example: 
 a. Renal insufficiency persists despite volume repletion b. Subject has new rash or signs of hypersensitivity (such as elevated eosinophil count) 7. Prior approval of Medical Monitor is required to re-initiate therapy if 
 c. Subject's serum creatinine has not returned to baseline d. There is evidence of thrombotic microangiopathy

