11.6 Acute Renal Failure

Acute renal failure and granulomatous interstitial nephritis have been reported in study participants receiving dabrafenib. In some cases, pyrexia may be associated with renal insufficiency/renal failure, possibly secondary to dehydration or hypotension. Renal function should be monitored carefully, especially in patients with pyrexia. Guidelines for the management of renal dysfunction can be found in Table 7.

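### Tables 4 and 7 of section 9.2.2 need reconciling: Table 7's two creatinine rows overlap, and the restart dose and the hold rule are not settled when fever and a creatinine rise coincide

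*Combined protocol and SAP*

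**What the plan says.** Section 9.2.2 gives fever and renal insufficiency separate tables and excludes both from the general toxicity table (Table 2).

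- **Table 7, first row.** The trigger is "For subjects with serum creatinine increase > 0.2 mg/dL but ≤ 0.5 mg/dL above baseline". Step 1 is "Continue dabrafenib and re-check serum creatinine within 1 week". Step 2 covers temperature of 38.5 C or more and sends the reader to the fever guidelines.
- **Table 7, second row.** The trigger is "For subjects with serum creatinine rise > 0.5 mg/dL above baseline or serum creatinine > 2 mg/dL". Step 1 interrupts the drug, and step 2 again refers fever to the fever guidelines. Step 5 says that, once creatinine is back to baseline, the investigator "may restart study treatment at the same dose, or reduced by one dose level at the investigator's discretion".
- **Table 4, complicated fever.** The drug is interrupted at once and held until the fever and accompanying symptoms resolve. Then: "At rechallenge reduce dose of dabrafenib by one dose level".
- **Table 4, uncomplicated fever.** The drug is held until the fever resolves, then restarted at the original dose or one level lower.

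Section 11.5 sends pyrexia to Table 4 and section 11.6 sends renal dysfunction to Table 7. Section 11.6 also says that "pyrexia may be associated with renal insufficiency/renal failure, possibly secondary to dehydration or hypotension". No passage says which table, or which row of Table 7, takes precedence when more than one applies.

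**The concern.** The protocol itself expects fever and renal impairment to occur together, and Table 4 calls for serum creatinine in the fever work-up. Managing a fever can therefore produce a Table 7 finding in the same patient. If the applicable rules point in different directions, two investigators who both follow the protocol could handle the same patient differently.

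At stake are patient safety, in a toxicity that section 11.6 links to acute renal failure, and the consistency of the dose received in a 23-patient, single-arm study. Toxicity is a secondary objective. The row overlap is separate from fever and would arise without it.

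**Working it through.** The plan gives no figure to reproduce here. The check is arithmetic for the row overlap and a side-by-side reading for the other two points.

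**1. Overlap of the Table 7 rows.** Let *b* be baseline creatinine and *r* the rise, both in mg/dL.

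- First row: 0.2 < r ≤ 0.5, with no limit on b + r.
- Second row: r > 0.5, or b + r > 2.0.
- Both rows apply when 0.2 < r ≤ 0.5 and b + r > 2.0. This requires b > 2.0 − r. Since r is at most 0.5, b must be strictly above 2.0 − 0.5 = 1.5.

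| Baseline (mg/dL) | Rises that meet both rows (to 0.01 mg/dL) |
|---|---|
| 1.5 or lower | none |
| 1.6 | 0.41 to 0.50 |
| 1.7 | 0.31 to 0.50 |
| 1.8 or higher | 0.21 to 0.50, i.e. every first-row rise |

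Example: 1.8 rising to 2.1 is a rise of 0.3 (first row, continue) and a value above 2 (second row, interrupt).

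Can such a baseline be enrolled? Section 6.1.9 accepts creatinine up to 1.5 × ULN, or clearance above 60 ml/min as an alternative. The documents do not give the ULN. Over an assumed range:

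| Assumed ULN (mg/dL) | 1.5 × ULN (mg/dL) |
|---|---|
| 1.0 | 1.50 |
| 1.1 | 1.65 |
| 1.2 | 1.80 |
| 1.3 | 1.95 |
| 1.4 | 2.10 |

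Any ULN above 1.0 makes the overlap reachable through the creatinine limit. The clearance alternative sets no creatinine limit, so it can also admit a baseline above 1.5.

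**2. Restart dose.** Take fever of 38.5 C or more with dehydration and a rise of 0.6 mg/dL, with creatinine later back to baseline.

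- Table 4: dehydration makes the fever complicated, so a one-level reduction is required.
- Table 7, second row: same dose or one level lower, at discretion.

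One table requires what the other makes optional. Without complicating signs, both tables allow the same or a reduced dose, so there is no conflict after uncomplicated fever.

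**3. Hold or continue.** Take fever of 38.5 C or more with a rise of 0.3 mg/dL to a value not above 2 mg/dL.

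- Table 7, first row, step 1: continue, with no exception for fever.
- Table 7, first row, step 2: manage the fever under the fever guidelines.
- Table 4: hold, whether the fever is complicated or not.

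Step 2 makes Table 4 the likely governing rule, but it does not withdraw step 1. In the second row the drug action is written out in step 1, ahead of a similar fever step, which suggests that step 1 is where Table 7 sets the drug action. The route to Table 4 is also not clean: the introductory text of section 9.2.2 assigns fever to Table 3 and neutropenia to Table 4, the reverse of the tables' own titles, while section 11.5 correctly points to Table 4. In the second row there is no such conflict, because both tables stop the drug.

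**The case against.** The strongest reply is that the tables are meant to be read together. Table 7 says what the creatinine rise alone requires, then passes febrile patients to the fever guidelines, which section 11.5 identifies as Table 4. This largely answers point 3. A reader might infer a flat contradiction, with Table 7 ordering treatment to continue through a fever for which Table 4 orders a hold; step 2 of the same row does not support that. What stands is a missing fever exception in step 1 and an unstated precedence.

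On restart dose, a one-level reduction satisfies both tables, and the second row also refers fever to the fever guidelines. That is fair, but Table 7 still expressly permits a restart that Table 4 does not allow after complicated fever.

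Neither reply touches the row overlap, which lies inside Table 7 and needs no fever. It is confined to baselines above 1.5 mg/dL.

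A reader might also infer a contradiction on NSAIDs, because Table 4 offers "acetaminophen 500 mg or ibuprofen 400 mg (or suitable alternative) prophylactically BID with study drug" and Table 7 adds "please note NSAIDs can induce renal insufficiency, especially in subjects with dehydration". The documents do not support that. Ibuprofen is one option beside acetaminophen or another alternative, Table 7 cautions without prohibiting, and in complicated fever the prophylaxis comes at restart, after accompanying symptoms such as dehydration are to have resolved.

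**Conclusion.** The point holds in a limited form, as three places where the text must be reconciled:

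1. The two rows of Table 7 overlap for a rise above 0.2 and up to 0.5 mg/dL to a value above 2 mg/dL. This is a direct conflict between continuing and interrupting.
2. After complicated fever with a second-row creatinine rise, Table 4 requires a reduction that Table 7 leaves optional.
3. The first row's continue step has no fever exception. Table 4 probably governs, but this is not stated.

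Point 1 matters in practice only if patients enter with creatinine strictly above 1.5 mg/dL. That rests on a ULN above 1.0 mg/dL (an assumption) or on entry through the clearance alternative, and on taking baseline to be the pretreatment value.

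The frequency of these combinations cannot be derived. Section 11.4 lists pyrexia at more than 10% and renal dysfunction at 1% to under 10%, and a reader might turn the pyrexia figure into a near-certain conflict among 23 patients. It counts any pyrexia, not fever of 38.5 C or more with a creatinine rise in a given band, and no joint frequency is given.

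The consequence is possible inconsistency in dosing and safety management. Sample size, error rates and the primary analysis are unaffected. Toxicities are tabulated by grade, which does not depend on which table drove the dose.

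**What to change.** - Make the two rows of Table 7 mutually exclusive, so that a value above 2 mg/dL with a rise of 0.5 mg/dL or less falls in only one of them.
- Add a line to Tables 4 and 7 stating which table decides hold or continue, and which decides the restart dose, when fever of 38.5 C or more and a creatinine rise occur together.
- While doing so, correct the swapped references to Tables 3 and 4 in the introductory text of section 9.2.2, so that the fever guidelines are identified without doubt.

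Which rule prevails is a clinical decision for the sponsor and safety team; this review takes no view on it. The cost is a wording amendment to two tables and one sentence, with no new procedures, visits or patients.

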9.3 Drug Interactions

9.3.1 Prohibited Medications

The pathways for metabolism and elimination of dabrafenib are presently unknown in humans. Preclinical *in vitro* data indicate that dabrafenib is primarily metabolized by CYP2C8, CYP3A4, and CYP2C19. Dabrafenib is also a substrate of two cell membrane drug transporter proteins; human P-glycoprotein (PGP) and murine breast cancer resistant protein 1 (BCRP1) *in vitro*. Drugs that are strong inhibitors or inducers of CYP3A, CYP2C8, PGP or BCRP1, are prohibited because they may increase or decrease dabrafenib concentrations, respectively (see Appendix B).

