9.3.2 Cautionary Medications

The following medications should be used with caution (see Appendix B):

- Drugs that are mild/moderate inhibitors or inducers of CYP3A, CYP2C8, PGP or BCRP because they may alter dabrafenib concentrations.

- *In vitro* dabrafenib inhibits CYP2C8, CYP2C9, and CYP2C19 activity. Concentration of medications metabolized by these enzymes may be altered by dabrafenib.
- *In vitro* dabrafenib induces CYP3A4, CYP2B6, CYP2C8, CYP2C9, and CYP2C19. Co-administration of dabrafenib and medications which are affected by the induction of these enzymes may result in loss of efficacy. If co-administration of these medications is necessary, investigators should monitor subjects for loss of efficacy or consider substitutions of these medications.

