APPENDIX B: Prohibited and Cautionary Medications

PROHIBITED MEDICATIONS	
Strong CYP2C8/3A/PGP/BCRP1 Inhibitor/Inducer. May alter levels of DABRAFENIB	Therapeutic Area
Clarithromycin, telithromycin, rifamycin class agents (e.g. rifampin, rifabutin, rifapentine), toleandomycin	Antibiotics
Itracozazole, ketoconazole, posaconazole, voriconazole	Antifungals
Nefazodone	Antidepressants
Gemfibrozil	Hyperlipidemia
Carbamazepine, phenobarbital, amiodarone, phenytoin, s-mephenytoin, bosentan, mibefradil, conivaptan	Miscellaneous
Cyclosporine	Immunosuppressive agents

CAUTIONARY MEDICATIONS	
CYP2C8/C9/C19 Substrates; these drugs may be altered (increased or decreased) by DABRAFENIB	Therapeutic Area
Cerivastatin	HMG-CoA Reductase Inhibitors
Tolbutamide, nateglinide, repaglinide	Antidiabetics
Amitriptyline, clomipramine, imipramine	Antidepressants
Mild/Moderate Inhibitor of CYP3A, CYP2C8, PGP and BCRP1; These drugs may increase concentrations of DABRAFENIB	
	Therapeutic Area
Erythromycin	Antibiotic
Fluconazole	Antifungal

Diltiazem, verapamil	Antiarrhythmics
Aprepitant, cimetidine, montelukast	Miscellaneous
Substrates of CYP3A4/CYP2B6/CYP2C8/CYP2C9/CYP2C19 that may be affected by induction by DABRAFENIB; These drugs may lose efficacy when co-administered with DABRAFENIB	
Therapeutic Area	
Chloramphenicol, doxycycline, erythromycin, moxifloxacin	Antibiotics
Caspofungin, fluconazole, terbinafine	Antifungals
Amlodipine, diltiazem, felodipine, nifedipine, nilvadipine, nisoldipine, verapamil	Antihypertensives
Aripiprazole, bupropion, buspirone, desipramine, haloperidol, mirtazapine, pimozide, quetiapine, trazodone	Antidepressants and Antipsychotics
Glyburide, saxagliptin, tolbutamide	Antidiabetics
Lamotrigine, valproate, divalproex, zonisamide,	Anticonvulsants
Alfentanil, buprenorphine, celecoxib, codeine, fentanyl, methadone, oxycodone	Analgesics
Aprepitant, cisapride, darifenacin, disopyramide, leflunomide, methohexital, oral contraceptives, quinine, ranitidine, sulfenacin, sulfasalazine, tramadol, tolvaptan	Miscellaneous
Alprazolam, brotizolam, diazepam, estazolam, midazolam, triazolam, zolpidem, zopiclone	Hypnotics and Sedatives
Diergotamine, ergotamine, eletriptan	Antimigraine agents
Everolimus, sirolimus, tacrolimus	Immunosuppressive agents
Astemizole, chlorpheniramine, ebastine	Antihistamine
Oral budesonide, methylprednisolone	Corticosteroids
Sildenafil, tadalafil, vardenafil	Erectile Dysfunction agents
Eplerenone	Selective Aldosterone Blockers

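### The rules on drugs that may alter dabrafenib levels leave out CYP2C19, one of three enzymes the protocol names as primary routes of its metabolism in vitro

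*Combined protocol and SAP*

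**What the plan says.** Section 9.3.1 opens with a caveat: "The pathways for metabolism and elimination of dabrafenib are presently unknown in humans". It then reports in vitro findings. For enzymes, "dabrafenib is primarily metabolized by CYP2C8, CYP3A4, and CYP2C19". For transporters, it names human P-glycoprotein and "murine breast cancer resistant protein 1 (BCRP1)".

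Two rules on dabrafenib exposure follow.

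- Prohibition (9.3.1): "Drugs that are strong inhibitors or inducers of CYP3A, CYP2C8, PGP or BCRP1, are prohibited". The stated reason is that these drugs may raise or lower dabrafenib concentrations.
- Caution (9.3.2, first bullet): "Drugs that are mild/moderate inhibitors or inducers of CYP3A, CYP2C8, PGP or BCRP because they may alter dabrafenib concentrations".

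Appendix B restates both. Its prohibited table is headed "Strong CYP2C8/3A/PGP/BCRP1 Inhibitor/Inducer. May alter levels of DABRAFENIB". Its cautionary section on drugs that raise dabrafenib levels names CYP3A, CYP2C8, PGP and BCRP1.

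CYP2C19 does appear in the other two bullets of 9.3.2, which describe what dabrafenib does to other drugs: "dabrafenib inhibits CYP2C8, CYP2C9, and CYP2C19 activity. Concentration of medications metabolized by these enzymes may be altered by dabrafenib", and "dabrafenib induces CYP3A4, CYP2B6, CYP2C8, CYP2C9, and CYP2C19".

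**The concern.** The protocol restricts interacting drugs because they may move dabrafenib concentrations up or down. That reasoning applies to any enzyme that metabolises the drug, yet one of the three enzymes described as primary is left out of the rules without comment. An investigator who applies 9.3 and Appendix B as written would find no instruction to be careful about dabrafenib exposure when a patient takes a drug that inhibits or induces CYP2C19.

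At stake are avoidable toxicity if exposure rises and unnoticed under-treatment if it falls. The second is harder to see here. Patients are free of disease at entry, so there is no tumour response to watch, and the research blood samples described in 10.2 are for germline DNA, exosomes and circulating tumour DNA, with no dabrafenib level mentioned.

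**Working it through.** No arithmetic beyond counting applies, and no sample size or error rate enters the point. The check sets the in vitro statement beside each place that governs dabrafenib levels.

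| Target named in 9.3.1 | 9.3.1 prohibition | 9.3.2 first bullet | Appendix B prohibited heading | Appendix B cautionary heading (dabrafenib levels) |
|---|---|---|---|---|
| CYP3A4 | yes (as CYP3A) | yes (as CYP3A) | yes (as 3A) | yes (as CYP3A) |
| CYP2C8 | yes | yes | yes | yes |
| CYP2C19 | no | no | no | no |
| PGP | yes | yes | yes | yes |
| BCRP1 | yes | yes (as BCRP) | yes | yes |

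**Coverage.** Two of three enzymes and two of two transporters are restricted, so four of five named targets. CYP2C19 is the only one missing. The two Appendix B columns restate the two rules, so the table shows one decision about scope written out at each level. It does not show four separate omissions.

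**Is CYP2C19 covered elsewhere?** Section 9.3 and Appendix B mention it five times. One mention is the metabolism statement. The other four are the second and third bullets of 9.3.2 and two Appendix B headings on substrates. All four concern the level or efficacy of the other drug. None says that the other drug may change the level of dabrafenib.

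**Does the strength of evidence explain the difference?** The caveat about human pathways applies equally to CYP3A4 and CYP2C8, which are restricted on the same in vitro data. A transporter described as murine is restricted too. Limited evidence alone therefore does not separate CYP2C19 from the targets that were kept.

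**Which drugs would be missed?** This cannot be answered from the documents. Some CYP2C19 inhibitors or inducers may already be listed in Appendix B because they act on another target. The documents do not classify any drug by its action on CYP2C19, so the gap is confined to drugs not listed for another reason and its size is unknown.

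**The case against.** The strongest reply is that the scope may be intended. The same four targets recur consistently, which fits a decision at least as well as an oversight. Whether CYP2C19 deserves a caution depends on its share of clearance, and section 5.1 refers readers to the Investigator's Brochure for detailed pharmacology. Restricting BCRP1 on in vitro data shows that such data can be enough for a restriction, but not that every in vitro route must be restricted. All of this stands, so a reader should not infer that the omission is a proven mistake.

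It can also be said that 9.3.1 itself discloses the CYP2C19 route just before the prohibition. That is correct: the pharmacology is stated, and what is missing is an instruction that acts on it.

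A reader might infer that screening for eligibility carries the gap forward through 6.2.4. The text does not support that as a reason for the change proposed here. That criterion excludes only current use of prohibited drugs and does not show that cautionary drugs are screened.

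The likely consequences are also limited. Treatment lasts four 28-day cycles, with a toxicity review, laboratory tests and an ECG each cycle. Table 1 permits reductions to 50 mg twice daily, one third of the full dose. Section 3.3 reports that no maximum tolerated dose was found and that 150 mg twice daily performed much like higher doses. These facts lower the stakes, but mainly for raised exposure. Comparison with higher doses says nothing direct about lowered exposure, and a toxicity review would not reveal it. The permitted reductions are deliberate and known, unlike a change caused by an unrecognised interaction.

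Finally, if CYP2C19 were treated like CYP3A and CYP2C8, its strong inhibitors and inducers would be prohibited. The documents give no contribution figure that would justify going so far, which is why a caution is the proportionate step.

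**Conclusion.** The point holds as a minor, cheap improvement. The protocol names CYP2C19 as a primary in vitro route of dabrafenib metabolism, but neither rule on dabrafenib levels covers it, and no reason is given. The result is that no rule cautions about exposure for CYP2C19 inhibitors or inducers that are not listed on other grounds.

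This rests on the protocol text alone and assumes that the Investigator's Brochure, which is not among the documents, does not rule CYP2C19 out as a relevant route. The relative contribution of CYP2C19, the change in exposure and the number of patients affected cannot be sized.

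Two stronger readings are tempting and unsupported. One is that patients will be materially over- or under-exposed: nothing shows that an effect through CYP2C19 alone would exceed the dose variation already permitted. The other is that the primary result is at risk: no effect on the rule of 9 relapse-free patients out of 23 can be derived, and none is claimed.

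**What to change.** Extend the first bullet of 9.3.2 so that, besides mild or moderate inhibitors and inducers of the four current targets, it covers inhibitors and inducers of CYP2C19 of any strength. The words on strength are needed because the prohibition does not cover CYP2C19, so its strong inhibitors and inducers would otherwise fall under neither rule. Add CYP2C19 to the matching cautionary section of Appendix B, worded to cover both inhibitors and inducers of that enzyme.

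Keep this as a caution. Leave the prohibited list and 6.2.4 unchanged, so eligibility is unaffected.

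The cost is one phrase in 9.3.2 and a small addition to Appendix B. The downside is that an occasional patient will need a review or substitution of a concomitant drug, possibly for an interaction that turns out not to matter.
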